# Table 3: Management of Ocular Disorders

	Tototot Version Bute. December 11, 2025				
Grade 3	
 
Complete eye exam as outlined in schedule of assessments (Study Calendar and Appendix C). Repeat complete exam as clinically indicated.
 
Patients should have weekly symptomatic ocular assessments until the symptoms resolve to Grade 1 or baseline or are deemed to be irreversible by the investigator.
 
Repeat complete exam as clinically indicated, at least every other cycle (from point at which toxicity first reported) at a minimum
 
	
 
Hold mirvetuximab soravtansine dosing.
 
Patients may be allowed to resume mirvetuximab soravtansine reduced by one dose level after AE has resolved to Grade 1 or better within 28 days.
 
			
Grade 4	
 
Complete eye exam as outlined in Study Calendar and Appendix C Repeat complete exam as clinically indicated.
 
Patients should have weekly symptomatic ocular assessments until the symptoms resolve to Grade 1 or baseline (Study Calendar and Appendix C) or are deemed to be irreversible by the investigator.
 
Repeat complete exam as clinically indicated, at least every other cycle (from point at which toxicity first reported) at a minimum
 
	Permanently discontinue mirvetuximab soravtansine dosing.			
* Appendix C includes CTCAE version 5.0 Grade definitions for select ocular disorders					

### 6.1.2 Monitoring of Non-Infectious Pneumonitis Following the Administration of Study Treatment

Non-infectious pneumonitis has been observed following the administration of mirvetuximab soravtansine and pembrolizumab and may result in fatigue, shortness of breath, cough or respiratory distress. Drug-induced pneumonitis may be immediately life-threatening. If a patient presents with signs or symptoms consistent with pneumonitis and/or a clinically meaningful change in pulse oximetry value, the patient should be immediately evaluated. Patients are advised to notify their treating physician immediately if they experience new or worsening shortness of breath, cough or respiratory distress.

For patients diagnosed with pneumonitis without an infectious etiology, the management and treatment guidelines outlined in Table 4 should be followed.

## **Table 4: Management of Pneumonitis**

	CTCAE v5.0 Severity	Dose Modifications	irAE management	Monitor and follow-
--	---------------------	---------------------------	-----------------	---------------------

Grade		with corticosteroid and/or other therapies	up
Grade 1	Continue dosing after discussion with the Overall PI		
Grade 2	Withhold mirvetuximab soravtansine and pembrolizumab (both agents) Mirvetuximab soravtansine can be resumed at a dose reduced by one dosing level (see Table 6), and pembrolizumab can be resumed at same dosing level after discussion with the Overall PI when symptoms resolve to ≤ Grade 1	Administer corticosteroids (initial dose of 1-2 mg/kg prednisone or equivalent) followed by taper*	
 
Monitor participants for signs and symptoms of pneumonitis
 
Evaluate participants with suspected pneumonitis with radiographic imaging and initiate corticosteroid treatment
 
Add prophylactic antibiotics for opportunistic infections
 

Grade 3 or 4, or recurrent Grade 2	Permanently discontinue mirvetuximab soravtansine and pembrolizumab (both agents)	Administer corticosteroids (initial dose of 1-2 mg/kg prednisone or equivalent) followed by taper*	
 
Monitor participants for signs and symptoms of pneumonitis
 
Evaluate participants with suspected pneumonitis with radiographic imaging and initiate corticosteroid treatment
 
Add prophylactic antibiotics for opportunistic infections
 

\* Notes on steroids for irAE:

1. Corticosteroid taper should be initiated upon AE improving to Grade 1 or less and continue to taper over at least 4 weeks.

 Pembrolizumab and mirvetuximab soravtansine can be resumed after AE has been reduced to Grade 1 or 0 and corticosteroid has been tapered. Both agents should be permanently discontinued if AE does not resolve within 12 weeks of last dose or corticosteroids cannot be reduced to ≤10 mg prednisone or equivalent per day within 12 weeks.

**3.** For severe and life-threatening irAEs, IV corticosteroid should be initiated first followed by oral steroid. Other immunosuppressive treatment should be initiated if irAEs cannot be controlled by corticosteroids.

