#### 6.3 **Re-treatment Criteria**

For a patient to begin a new cycle or continue a cycle of therapy after a dose modification, the following criteria must be met.

- Pre-treatment criteria as described in Section 5.2.2 with the following exceptions
  - $\circ$  Treatment-emergent ocular disorders, which must have recovered to  $\leq$  Grade 1 or baseline
  - $\circ$  Treatment-emergent pneumonitis which must have recovered to  $\leq$  Grade 1

If the patient does not meet these criteria, dosing with the two agents in the combination regimen will be delayed and the patient should be re-evaluated within 48-72 hours. Dosing with both agents may resume if these criteria have been met. If the adverse event can be attributed to one of the agents in the combination regimen, that agent will be held or discontinued as per the Dose Modification Guidelines

described in Sections 6.1 and 6.2 respectively; however, treatment with the second agent may resume provided all the other criteria are met. However, if the next cycle is delayed due to treatment-related toxicity longer than 12 weeks then the patient should be removed from study treatment. In such cases, continuation of study treatment may be considered for those patients who have experienced clinical benefit if agreed upon between the Overall PI and the Investigator.

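### Restart after Grade 2 pneumonitis depends on grade alone in two places and also on an undefined steroid taper in two others, so the permitted restart can differ by anything from about zero to 28 days or more

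*Combined protocol and SAP*

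**What the plan says.** Four places in the protocol govern restart after Grade 2 pneumonitis.

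- **Table 4, Grade 2 row, dosing cell.** Both agents are withheld. Mirvetuximab soravtansine may then resume one dose level lower, and "pembrolizumab can be resumed at same dosing level after discussion with the Overall PI when symptoms resolve to ≤ Grade 1". The cell has no steroid condition. The neighbouring steroid cell calls for corticosteroids ("initial dose of 1-2 mg/kg prednisone or equivalent) followed by taper") and carries an asterisk to the notes below the table.
- **Table 4, notes 1 and 2.** Note 1: "Corticosteroid taper should be initiated upon AE improving to Grade 1 or less and continue to taper over at least 4 weeks". Note 2: "Pembrolizumab and mirvetuximab soravtansine can be resumed after AE has been reduced to Grade 1 or 0 and corticosteroid has been tapered". Note 2 goes on to require permanent discontinuation if the event has not resolved within 12 weeks of the last dose, or if the steroid cannot be brought to 10 mg/day prednisone or less within 12 weeks.
- **Table 7, instruction 2.** This gives the same two-part condition (grade and taper) for pembrolizumab. The pneumonitis row of Table 7 sends the reader back to Table 4.
- **Section 6.3, Re-treatment Criteria.** This applies the Section 5.2.2 criteria with a stricter grade for two events, one of them "Treatment-emergent pneumonitis which must have recovered to" Grade 1 or less. If the criteria are not met, the patient is re-evaluated within 48 to 72 hours. Then: "Dosing with both agents may resume if these criteria have been met". No steroid condition is stated.

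**The concern.** Under note 1, reaching Grade 1 or less is when the taper begins. Under the Grade 2 row and Section 6.3, the same moment satisfies the stated pneumonitis condition for restart. Someone working from Section 6.3 or the dosing cell can therefore re-dose both drugs at a point where note 2, on most readings of *tapered*, does not yet allow it.

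This matters because pneumonitis is the adverse event of special interest for mirvetuximab soravtansine (Section 7.6.3), has been observed with both agents, and is described in Section 6.1.2 as possibly life-threatening. A recurrent Grade 2 event means permanent discontinuation of both drugs. If restart timing varies with the passage used, so do post-event exposure, steroid cover at re-challenge and the recurrence data.

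**Working it through.** The plan gives no figure to reproduce. The check compares the passages and derives the resulting gap. Day 0 is the day the pneumonitis first reaches Grade 1 or less.

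**Step 1: conditions side by side**

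| Place | Grade condition | Steroid condition | Other |
|---|---|---|---|
| Table 4, Grade 2 row | Grade 1 or less | none in the dosing cell | Overall PI discussion |
| Section 6.3 | Grade 1 or less | none | Section 5.2.2 criteria |
| Table 4, note 2 (both agents) | Grade 1 or 0 | has been tapered | none stated |
| Table 7, instruction 2 (pembrolizumab) | Grade 1 or 0 | has been tapered | none stated |

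The grade conditions agree. Only the steroid condition differs.

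**Step 2: does another passage supply the steroid condition?** Section 5.2.2 has no steroid criterion. Section 5.4.3 allows systemic glucocorticoids for events of suspected immunologic origin, so being on steroids does not itself bar dosing. Section 6.3 refers back to Sections 6.1 and 6.2 for an event attributed to one agent. The Grade 2 row withholds both agents, so that referral does not clearly bring in note 2.

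**Step 3: size of the gap**

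Inputs: taper starts on day 0 and lasts at least 4 weeks = 28 days (note 1); initial steroid dose 1 to 2 mg/kg (Grade 2 row); only stated steroid threshold 10 mg/day (note 2); cycle length 21 days (Section 5.1).

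- Row or Section 6.3 read alone: earliest restart is day 0, subject to the other conditions in the table above.
- Note 2, *tapered* = begun: earliest restart is close to day 0. Gap close to zero.
- Note 2, *tapered* = completed: earliest restart is day 28 or later. Gap at least 28 days, and 28/21 = 1.33 cycles.
- Note 2, *tapered* = at or below 10 mg/day: the day depends on the taper schedule, which the protocol does not give. For illustration, **assume** a linear 28-day taper to zero and body weight of 50 to 100 kg (neither is in the documents). The day on which 10 mg/day is reached is 28 × (1 − 10/starting dose).
  - Lowest starting dose: 1 mg/kg × 50 kg = 50 mg, giving 28 × (1 − 10/50) = 22.4 days.
  - Highest starting dose: 2 mg/kg × 100 kg = 200 mg, giving 28 × (1 − 10/200) = 26.6 days.

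**Step 4: how many patients?** Table 8 lists pneumonitis of Grade 2 or less in 34 of 404 patients given mirvetuximab soravtansine (34/404 = 8.4%). This pools Grade 1, for which Table 4 does not call for a hold, with Grade 2, and it does not give the contribution of pembrolizumab. The number of Grade 2 events to expect among 35 patients cannot be obtained from it.

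**The case against.** The strongest reply is that the passages are cumulative. The notes belong to Table 4, the asterisk in the Grade 2 row leads to them, and Section 6.1.2 directs that Table 4 be followed. Table 7 repeats the taper condition for pembrolizumab, and nowhere is a taper called unnecessary. Section 6.3 introduces its list as conditions that must be met, and its permission is only that dosing *may* resume. Treating Section 6.3 as self-sufficient would also prove too much: a Grade 3 event that recovered to Grade 1 could be re-dosed despite the permanent discontinuation in Table 4. Finally, the row requires discussion with the Overall PI, which puts a central decision-maker in the path of restart.

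Much of this stands. A reader might infer that note 2 cannot be an added condition because Section 6.3 is complete in itself; the documents do not support that. Central discussion also limits divergence between sites.

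Two things remain. The asterisk sits on the steroid cell and leads to notes about steroids, while the dosing cell reads as complete. Section 6.3, which is the dedicated re-treatment section and names pneumonitis, still gives a grade-only permission and does not itself require the PI discussion at restart. And even a fully cumulative reading leaves *tapered* undefined.

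**Conclusion.** The point holds as an incomplete and ambiguous restart condition. The Table 4 Grade 2 row and Section 6.3 omit a steroid condition that Table 4 note 2 and Table 7 instruction 2 impose, and the condition itself is undefined. The permitted restart can differ by close to zero days (taper begun), by about 22 to 27 days (10 mg/day or less, under the assumed linear taper and weights), or by 28 days or more (taper completed). The last two exceed one cycle.

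Two stronger readings are tempting. The first is that restart always differs by at least 4 weeks; that holds only if *tapered* means completed, which the protocol does not say. The second is that about 3 of 35 patients would be affected (0.084 × 35 = 2.9); the Table 8 rate cannot support this, for the reasons in step 4.

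No endpoint, sample size or analysis rule changes. The consequence is for safety management and for consistent safety data, which makes this worth correcting.

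**What to change.** Reconcile the Table 4 Grade 2 row, Table 4 notes 1 and 2, Table 7 instruction 2 and Section 6.3 so that all state the same restart condition for pneumonitis. The text should say whether a steroid condition applies and, if it does, define *tapered* (begun, at or below a stated level, or completed). A cross-reference from Section 6.3 to the agreed condition would keep the passages aligned. The sponsor's clinical team must decide the rule; this review does not say which passage is right.

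The cost is a wording amendment, with no extra visits, tests or patients.

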### 6.1.3 Other symptoms

Mirvetuximab soravtansine dose may be reduced at the discretion of the Investigator after discussion with the Overall PI. Patients who develop adverse events requiring an interruption of mirvetuximab soravtansine may resume treatment at a reduced dose level as shown in Tables 5 and 6 provided the criteria outlined in Section 5.2 are met.

### **Table 5: Mirvetuximab Soravtansine Dose Modification Guidelines**

Adverse Event	Management/Next Dose for Mirvetuximab Soravtansine
≤ Grade 1	No change in dose
Grade 2	Hold until $\leq$ Grade 1. Resume at same dose level.
Grade 3	Holduntil < Grade 2. Resume at one dose level lower
Grade 4	Off protocol therapy

### **Table 6: Mirvetuximab Soravtansine Dose Levels**

Dose Level	Mirvetuximab Soravtansine Dose
-2	4 mg/kg AIBW, Q21 day
-1	5 mg/kg AIBW, Q21 day
0	6 mg/kg AIBW, Q21 day

A second dose reduction will be permitted for second event of Grade 3 or higher. Dose reductions below 4 mg/kg (Dose Level -2) will not be permitted.

Mirvetuximab soravtansine may be interrupted for situations other than treatment-related Aes such as medical / surgical events or logistical reasons not related to study therapy. Participants should be placed back on study therapy within 3 weeks of the scheduled interruption, unless otherwise discussed with the Overall PI. The reason for interruption should be documented in the patient's study record.

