## 5.2.2 Subsequent Cycles

- Absolute neutrophil count  $\geq$ 1,000/mcL
- Platelets  $\geq$ 75,000/mcL
- AST (SGOT) / ALT (SGPT)  $\leq 2.5$  x institutional upper limit of normal
- Creatinine ≤ institutional upper limit of normal or creatinine clearance >= 40 mL/min/1.73 m2 for subjects with creatinine levels above institutional normal
- All toxicities pf previous cycles must have resolved to  $\leq$  grade 2
- ECOG performance of 0 to 2
- No evidence of life-threatening medical problems

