#### DOSING DELAYS/DOSE MODIFICATIONS

Every effort should be made to administer study treatment on the planned dose and schedule.

Dose delays and modifications will be made as indicated in the following table(s). The descriptions and grading scales found in the revised NCI Common Terminology Criteria for Adverse Events (CTCAE) version 5.0 will be utilized for dose delays and dose modifications. A copy of the CTCAE version 5.0 can be downloaded from the CTEP website http://ctep.cancer.gov/protocolDevelopment/electronic\_applications/ctc.htm.

Patients experiencing AEs that can be clearly attributed to mirvetuximab soravtansine or pembrolizumab will have the corresponding agent modified or withheld. In case of an AE recurrence, the other drug in the combination regimen will then be modified or withheld. If a relationship of an AE to a particular drug cannot be clearly determined, the order in which the drugs are to be reduced will require approval from the Overall PI.

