### Attribution of Toxicity:

When study interventions are administered in combination, attribution of an adverse event to a single component is likely to be difficult. Therefore, while the investigator may attribute a toxicity event to the combination, to mirvetuximab soravtansine alone or to pembrolizumab alone, for adverse events listed in Table 7, both interventions must be held according to the criteria in Table 7 Dose Modification Guidelines for Pembrolizumab.

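### For a Grade 4 second event handled under Section 6.1.3, Table 5 ends protocol therapy but the note under Table 6 permits mirvetuximab at 4 mg/kg

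*Combined protocol and SAP*

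**What the plan says.** All references are to the combined protocol and SAP.

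- **Section 6, opening text.** Patients with an event clearly attributed to one agent "will have the corresponding agent modified or withheld".
- **Section 6.1.3.** A mirvetuximab dose may be reduced at the investigator's discretion after discussion with the Overall PI. Patients whose adverse event required an interruption "may resume treatment at a reduced dose level as shown in Tables 5 and 6 provided the criteria outlined in Section 5.2 are met".
- **Actions by grade, Table 5.** Grade 3: hold, then resume one level lower. Grade 4: "Off protocol therapy", whether it is a first or a later event.
- **Table 6.** Level 0 is 6 mg/kg, level -1 is 5 mg/kg and level -2 is 4 mg/kg, all by adjusted ideal body weight every 21 days. The note beneath says: "A second dose reduction will be permitted for second event of Grade 3 or higher". The sentence after it bars any dose below 4 mg/kg.
- **Section 5.2.2.** "All toxicities pf previous cycles must have resolved to" Grade 2 or less before a subsequent cycle.
- **Section 6.3.** Re-treatment requires "Pre-treatment criteria as described in Section 5.2.2 with the following exceptions"; the exceptions cover only ocular disorders and pneumonitis.

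Some events are handled elsewhere: mirvetuximab infusion reactions (Table 1), ocular events (Table 3), pneumonitis (Table 4) and immune-related events (Table 7). Section 6.2 says that, whatever the attribution, "for adverse events listed in Table 7, both interventions must be held according to the criteria in Table 7". None of these is part of this point.

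**The concern.** Section 6.1.3 makes Tables 5 and 6 operate together, yet on one sequence of events they give different answers about whether the patient may receive the conjugate again. Table 5 closes the door at Grade 4. The note under Table 6 leaves it open when the Grade 4 event is the second one.

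What is at stake is a stopping rule for severe toxicity in a multi-center trial. Someone relying on Table 5 ends protocol therapy. Someone relying on the note can propose re-exposure after a Grade 4 toxicity and point to the protocol as authority. It also becomes unclear whether such re-dosing is a protocol departure, and Appendix B, Section 3.9.1 requires all departures to be reported.

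**Working it through.** The plan states no figure to reproduce here. The check sets the texts side by side along the possible sequences of events.

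**Inputs.** Dose ladder 6, 5, 4 mg/kg (Table 6); actions by grade (Table 5); second-reduction permission and 4 mg/kg floor (text under Table 6); resumption criteria (Sections 5.2.2 and 6.3).

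**Step 1: what the note covers.** It applies to a second event of Grade 3 or above. In CTCAE, Grade 5 is death, so for a patient who could be dosed again the grades covered are 3 and 4.

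**Step 2: sequences, starting from 6 mg/kg.**

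| Events, in order | Table 5 | Text under Table 6 | Result |
|---|---|---|---|
| Grade 3, Grade 3 | 6 to 5, then 5 to 4 mg/kg | second reduction, to 4 mg/kg | agree |
| Grade 4 first | stop | not reached: no second event | no conflict |
| Grade 3, Grade 4 | 6 to 5 mg/kg, then stop | second reduction permitted, 5 to 4 mg/kg | **conflict** |
| Grade 3, Grade 3, Grade 4 | 6 to 5 to 4 mg/kg, then stop | floor reached, no further reduction | no conflict |

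A patient can also be at 5 mg/kg for other reasons: a discretionary reduction (Section 6.1.3), an ocular event (Table 3) or Grade 2 pneumonitis (Table 4). Whether a later Grade 4 event then counts as the second event depends on how the note is read. The table is therefore not a full list of histories, and no fraction should be taken from it.

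**Step 3: size of the dose at issue.** On the conflicting sequence the next dose is 0 under Table 5, or as much as 4 mg/kg under the note. That is 4/5 = 80% of the dose that preceded the Grade 4 event, and 4/6 = 66.7% of the starting dose.

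**Step 4: does other text settle it?**

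- Section 5.2.2 tests the grade after recovery, not the worst grade. A Grade 4 event that has fallen to Grade 2 passes.
- Section 6.3 repeats those criteria for events that are neither ocular nor pneumonitis, then refers back to Sections 6.1 and 6.2, where the conflict sits. Its 12-week limit concerns length of delay, not severity.
- The opening of Section 6 says that if an event recurs, the other drug is then modified or withheld. That does not say whether mirvetuximab may be given again, and it does not reach a second event of a different kind.
- No sentence ranks Table 5 above the note or limits the note to Grade 3.

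**The case against.** The strongest reply is that the two texts do different jobs. Section 6.1.3 concerns patients whose event led to an interruption and who "may resume treatment at a reduced dose level as shown in Tables 5 and 6". Under Table 5 a Grade 4 event is an exit, not an interruption. Table 5 would then decide whether dosing resumes, and Table 6 only how far down it may go. Table 5 gives recovery thresholds for Grades 2 and 3 but none for Grade 4, which also suggests that no return was intended. This is probably what the authors meant. It works, however, only if the words *or higher* in the note do nothing, and the protocol does not say that they do nothing.

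A second reply stands in part. The note permits and does not require. Section 6.1.3 calls for discussion with the Overall PI before a discretionary reduction, and Section 5.5 allows therapy to stop for unacceptable adverse events. A reader might infer that sites will act in opposite ways unchecked, or that the protocol directs re-dosing after Grade 4. The documents support neither inference, because a central discussion is provided for and the wording is permissive. That discussion still lacks a rule to apply.

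A reader might also infer that every Grade 4 event is affected, that a set share of patients or sequences is, or that the co-primary results are at risk. The first is contradicted by Step 2 and by the separate tables. For the others, the documents give no rate for this sequence, and the decision rules in Section 13.1 do not depend on it.

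**Conclusion.** The inconsistency is real and narrow, and it should be corrected. For a mirvetuximab-attributed event under Section 6.1.3, a patient at 5 mg/kg whose second event is Grade 4 must stop under Table 5 and may receive 4 mg/kg under the note, with no stated precedence.

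This rests on two assumptions: that *or higher* carries its ordinary meaning, and that the patient has had one reduction, as the term second reduction implies. The importance lies in the clarity of a safety stopping rule. No frequency and no effect on sample size, error rates or the co-primary tests is claimed.

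The protocol's own pattern favours the stop. Grade 4 ends mirvetuximab for infusion reactions (Table 1), ocular events (Table 3) and pneumonitis (Table 4), so the note is the outlier. The documents do not show whether the exception was deliberate.

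**What to change.** Replace the sentence on the second reduction under Table 6 with:

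> *For events managed under Table 5, one further dose reduction is allowed after a second Grade 3 event; Grade 4 events end protocol therapy as stated in Table 5. Infusion reactions, ocular events, pneumonitis and immune-related events of any grade follow Tables 1, 3, 4 and 7 respectively.*

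Keep the 4 mg/kg floor sentence and all tables as they are. The cross-references need to cover every grade, not only Grade 4. Grade 3 pneumonitis (Table 4) and Grade 3 mirvetuximab infusion reactions (Table 1) also require permanent discontinuation, and an unqualified permission for Grade 3 would overlap with those stops.

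The cost is one sentence, with no added data or patients. The investigator loses the option of 4 mg/kg after a Grade 4 second event that reverses quickly. If the sponsor wants to keep that option, it should be written into Table 5 as an explicit exception with its own recovery threshold.
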